5.6.3. Clinical laboratory evaluation

Not Applicable

CONFIDENTIAL	STATISTICAL ANALYSIS PLAN N° GDX-44-016 VERSION N° 4.0 (REF I011622)	F015830-03 Page 29 / 35
--------------	--	----------------------------

5.6.4. Vital signs, physical findings and other observations related to safety

Not Applicable.

5.6.5. Concomitant medications and procedures

Concomitant medications will be coded using the latest WHO Drug dictionary version in force at the date of data base lock. Incidence of concomitant medications will be tabulated. The number and percent of patients taking concomitant medications will be presented. The denominator will be the number of patients in the SS.

Summary tables (number and % of patients) grouped by the first and the last level of ATC code will be presented whatever the purpose and when purpose is only for AEs (purpose coded 2), respectively. Concomitant medications are those ongoing (“Start Period” coded 2) after IMPs administration.

Listing of all concomitant medications will be presented in CSR appendix 16.2.4.

Concomitant procedures will be coded in System Organ Class (SOC) and Preferred term (PT) using the MedDRA version in force at the time of the Database lock. Incidence of concomitant procedures will be tabulated. The number and percent of patients undergoing concomitant procedures will be presented. The denominator will be the number of patients in the SS.

Summary tables (number and % of patients) grouped by SOC and PT will be presented when the “Start Date” of the procedure is superior or equal to the date of IMPs administration.

Listing of all concomitant medications and procedures will be presented in CSR appendix 16.2.4.

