6 CONCOMITANT MEDICATIONS / PROCEDURES

6.1 Concomitant Medications

Any medication, including homeopathic products, premedication, over-the-counter medications, as well as prescription drugs, on-going at the time of patient's informed consent signed or administered during the trial will be recorded in the patient's eCRF. The following information must be provided:

- Drug (brand name or generic name)
- Route of administration
- Purpose (medical history/trial disease/AE/pre-medication/contraception/prophylaxis)
- Indication
- Start/end period: before administration, after administration, ongoing at the end of the trial.

6.1.1 *Concomitant Medications of Special Attention*

Currently, no treatment has been identified that is capable of preventing an allergic reaction with any GBCA. Thus, no pre-treatment of any nature will be recommended before contrast-enhanced MRI. Nevertheless, if the investigator decides to premedicate a patient, the treatment must be documented in the medical file and then in the clinical eCRF.

Beta-blockers, vasoactive substances, angiotensin-converting enzyme inhibitors, angiotensin II receptor antagonists: these medicinal products decrease the efficacy of the mechanisms of cardiovascular compensation for blood pressure disorders: the radiologist must be informed before injection of gadolinium complexes, and resuscitation equipment must be at hand.

According to current knowledge, there is no other concomitant treatment of special attention in that trial. However, warnings and precautions for use of the concomitant treatments taken by the patient should be considered.

6.1.2 *Prohibited Concomitant Medications*

Any contrast agent (MRI or CT) within 3 days prior to trial products administration and during the course of the trial or within 24 hours after the trial product administration are prohibited.

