2.1.5. Prior medications and procedures

Prior medications and procedures / therapeutic measures are defined as medications and procedures ended before the first administration of IMPs. Prior medications and procedures / therapeutic measures will be coded using the Anatomical Therapeutic Chemical (ATC) World Health Organisation (WHO) Drug dictionary and MedDRA latest version in force at the time of data base lock, respectively.

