5.4.5. Prior medications and Procedures

Summary tables (number and % of patients) grouped by ATC codes (Version WHO Drug September 2024) will be presented for prior medications (those with “End of Treatment” coded 1) and by SOC and PT for prior procedures (those with “End Date” of the procedure inferior to the date of the IMPs administration).

The tables will be sorted according to the percentage of patients reporting at least one previous medication / at least one previous procedure from the most to the least frequent globally.

Listing of all medications and procedures will be presented in CSR Appendix 16.2.4.

CONFIDENTIAL	STATISTICAL ANALYSIS PLAN N° GDX-44-016 VERSION N° 4.0 (REF I011622)	F015830-03 Page 23 / 35
--------------	--	----------------------------

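### The SAP's prior and concomitant rules do not cover every treatment: procedures spanning the injection fall in neither summary table, and the medication rule selects ongoing drugs by a start code that cannot identify them

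*SAP*

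**What the plan says.** SAP 2.1.5 treats as prior those treatments "defined as medications and procedures ended before the first administration of IMPs". SAP 5.4.5 turns this into selection rules. Prior medications are the records with End of Treatment coded 1, and prior procedures are "those with “End Date” of the procedure inferior to the date of the IMPs administration".

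SAP 5.6.5 gives the rules for the other class. For drugs: "Concomitant medications are those ongoing (“Start Period” coded 2) after IMPs administration". For procedures, the summary tables "will be presented when the “Start Date” of the procedure is superior or equal to the date of IMPs administration". SAP 2.3.5 names only the coding dictionaries and adds no definition of concomitant.

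The collected categories for drugs are in Protocol 6.1: "Start/end period: before administration, after administration, ongoing at the end of the trial". The same section requires medication already being taken at consent to be recorded. Protocol 11.3.4 lists concomitant treatments and concomitant procedures among the baseline characteristics shown by arm, with the treatments tabulated by ATC code.

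**The concern.** The two classes are defined on different variables: prior on when the treatment ended, concomitant on when it started. Rules of that kind leave a hole for anything that starts before the injection and ends after it, which is the pattern of long-term therapy.

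At stake is what the summary tables can show. Tables 14.1.4.13 to 14.1.4.16 would give treatments already stopped. Tables 14.3.6.1 and 14.3.6.2 would give treatments newly started. Treatment in effect at the MRI and through the safety follow-up could be absent from both sets, so its balance between arms could not be read from a table. The count of patients on concomitant medication would mean only those who began a drug after the injection. The classes that Protocol 6.1.1 marks for special attention, such as beta-blockers and angiotensin-converting enzyme inhibitors, would fall in the hole whenever they are taken long term.

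**Working it through.** The plan states no figure on this point, so there is nothing to reproduce. The check runs each possible start/end pattern through the rules of SAP 5.4.5 and 5.6.5.

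**Procedures and therapeutic measures** (days relative to the IMP date, day 0). Prior: End Date < 0. Concomitant: Start Date ≥ 0.

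| Start | End | Prior | Concomitant |
|---|---|---|---|
| -3 | -1 | yes | no |
| -3 | 0 | no | no |
| -3 | +1 | no | no |
| -3 | ongoing | no | no |
| 0 | 0 | no | yes |
| 0 | +1 | no | yes |
| +1 | +1 | no | yes |

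Every pattern that starts before day 0 and ends on day 0 or later meets neither rule. No code list is needed to see this.

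**Medications.** Prior: End of Treatment = 1. Concomitant: Start Period = 2. The meaning of the codes has to be inferred, so take the possible readings in turn.

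*Reading A: 1 = before, 2 = after, 3 = ongoing at the end of the trial* (the Protocol 6.1 order, numbered from 1).

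| Start | End | Prior | Concomitant by the code | Concomitant by the word ongoing |
|---|---|---|---|---|
| before | before | yes | no | no |
| before | after | no | no | yes |
| before | ongoing at end | no | no | yes |
| after | after | no | yes | yes |
| after | ongoing at end | no | yes | yes |

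Two of the five patterns are in no table, and for both of them the sentence and its code disagree.

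*Reading B: Start Period 2 = started before.* A drug that both started and stopped before injection would be in the prior and the concomitant tables at once. Drugs started after injection (the last two rows) would be in neither. That would defeat the table in SAP 5.6.5 restricted to drugs given for adverse events.

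*Reading C: numbering from 0, so 2 = ongoing at the end.* This is not a start period. If it were used as one, drugs taken past the injection but stopped before the end of the trial would be missed. End of Treatment 1 would also then mean after administration, against SAP 2.1.5.

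Reading A is the most plausible. It agrees with End of Treatment 1 meaning ended before, and it leaves the adverse-event table usable. But no reading of a single start code separates the records correctly.

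**After the change.** Let concomitant mean not ended before administration. Of the five medication patterns, 1 is prior and 4 are concomitant (1 + 4 = 5). Of the seven procedure patterns, 1 is prior and 6 are concomitant (1 + 6 = 7). None is in both classes or in neither.

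**The case against.** The strongest reply concerns medications. The SAP sentence says ongoing, and a drug continued through injection is ongoing, so on the wording it counts. The exclusion comes from a code whose meaning neither document prints. End of Treatment and Start Period are different fields, so a code cannot simply be carried from one to the other. SAP 5.6.5 also codes the adverse-event purpose as 2, although that purpose stands third in the Protocol 6.1 list, so at least one code does not follow the printed order numbered from 1.

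This stands as far as it goes. A reader might infer that the SAP plainly restricts concomitant drugs to those started after injection. The documents do not establish that; it is the likelier reading of a sentence whose words point the other way. What the reply does not rescue is the filter, which gives a wrong table under every reading above.

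For procedures, one can say that many are single-day events, that participation lasts only 2 to 9 days, and that Protocol 6.2 marks concomitant procedures as not applicable. The gap may therefore hold few records. Yet Protocol 8.1.2 and 8.1.3 ask for procedures and therapeutic measures to be documented, and the SAP tabulates them. The titles of Tables 14.1.4.15 and 14.1.4.16 could take in a measure begun between consent and injection, but the selection rule in SAP 5.4.5 is narrower.

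Background medication is not wholly absent either. Tables 14.1.4.11 and 14.1.4.12 give the number and percentage of patients with a medical history under medication. They are not specified by drug class, so they do not fill the gap.

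**Conclusion.** The rules do not partition the records. For procedures and therapeutic measures this is explicit in the SAP's own date rules. For medications the sentence in SAP 5.6.5 and its selection code do not agree. Under the most plausible reading, drugs begun before and continued through the injection are in neither table. That reading is an inference to be confirmed against the eCRF.

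The effect is confined to descriptive tables: 14.1.4.13 to 14.1.4.16 and 14.3.6.1 to 14.3.6.2. The records themselves stay in Listings 16.2.4.5 and 16.2.4.6.

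Two stronger conclusions are tempting and not supported. One is a count of affected patients: the documents give no frequency of continuing treatment, so none can be derived. The other is that the efficacy result is at risk. The SAP plans no covariate adjustment and no subgroup examination (3.4 and 3.11), and neither the primary endpoint nor the adverse event tables use the concomitant-treatment class. The correction is still worth making, because the reported concomitant counts would otherwise not mean what their labels say.

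**What to change.** In SAP 5.6.5:

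- Define a concomitant medication as any record whose End of Treatment is not before administration, whatever its start period. Confirm the End of Treatment and Start Period codes against the eCRF and print them in the SAP.
- Define a concomitant procedure or therapeutic measure as one whose End Date is on or after the IMP date, or which is ongoing.

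Leave the prior rule in SAP 2.1.5 and 5.4.5 unchanged. Each record with its period or dates filled in then falls in exactly one class. If it is useful to see what was newly started, the concomitant tables can be split into started before and started after injection.

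The cost is two sentences, a changed programming filter and a check of the code list. No new data are needed.

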6. LIST OF TABLES, FIGURES AND LISTINGS

6.1. Contents of clinical study report section 14

14.1 DEMOGRAPHIC DATA

14.1.1 DISPOSITION OF PATIENTS

- Table 14.1.1.1 Number of Patients in Each Data Set – Screened Patient Set (SPS)
- Table 14.1.1.2 Patient Overall Disposition – Screened Patient Set (SPS)
- Table 14.1.1.3 Patient Disposition by Visit – Screened Patient Set (SPS)
- Table 14.1.1.4 Number of Patients by Center – Screened Patient Set (SPS)
- Table 14.1.1.5 Reasons for Screen-Failure – Screened Patient Set (SPS)
- Table 14.1.1.6 Reasons for Premature Discontinuation –All Randomized Patient Set (ARPS)

14.1.2 PROTOCOL DEVIATIONS

- Table 14.1.2.1 Protocol Deviations – Screened Patient Set (SPS)
- Table 14.1.2.2 Major Protocol Deviations – Screened Patient Set (SPS)
- Table 14.1.2.3 Non-major Protocol Deviations – Screened Patient Set (SPS)

14.1.3 DATA SETS ANALYSED

See Table 14.1.1.1.

14.1.4 DEMOGRAPHICS AND BASELINE CHARACTERISTICS

- Table 14.1.4.1 Demographic Characteristics at Screening Visit (V1) – Off-site FAS
- Table 14.1.4.2 Demographic Characteristics at Screening Visit (V1) –Off-site PPS
- Table 14.1.4.3 Study Disease – Diagnosis of The Glioma At Screening Visit (V1) –Off-site FAS
- Table 14.1.4.4 Study Disease – Diagnosis of The Glioma At Screening Visit (V1) –Off-site PPS
- Table 14.1.4.5 Grade of the primary glial tumor by treatment arm assigned at randomization and by grade (stratification variable at randomization) At Screening Visit (V1) –Off-site FAS
- Table 14.1.4.6 Grade of the primary glial tumor by treatment arm assigned at randomization and by grade (stratification variable at randomization) At Screening Visit (V1) –Off-site PPS

CONFIDENTIAL	STATISTICAL ANALYSIS PLAN N° GDX-44-016 VERSION N° 4.0 (REF I011622)	F015830-03 Page 30 / 35
--------------	--	----------------------------

Table 14.1.4.7	Imaging History At Screening Visit (V1) –Off-site FAS
Table 14.1.4.8	Imaging History At Screening Visit (V1) –Off-site PPS
Table 14.1.4.9	Medical History At Screening Visit (V1) –Off-site FAS
Table 14.1.4.10	Medical History At Screening Visit (V1) –Off-site PPS
Table 14.1.4.11	Medical History Under Medication at Screening Visit (V1) –Off-site FAS
Table 14.1.4.12	Medical History Under Medications at Screening Visit (V1) –Off-site PPS
Table 14.1.4.13	Prior Medications According to ATC System Main Group –Off-site FAS
Table 14.1.4.14	Prior Medications According to ATC System Main Group –Off-site PPS
Table 14.1.4.15	Procedures Undergone Between Informed Consent Signature And Administration of IMPs By System Organ Class And Preferred Term –Off-site FAS
Table 14.1.4.16	Procedures Undergone Between Informed Consent Signature And Administration of IMPs By System Organ Class And Preferred Term –Off-site PPS
Table 14.1.4.17	Serum Creatinine Results And eGFR At Screening Visit (V1) - Off-site FAS
Table 14.1.4.18	Serum Creatinine Results And eGFR At Screening Visit (V1) –Off-site PPS
Table 14.1.4.19	Serum Creatinine Results And eGFR At Screening Visit (V1) - Safety Set (SS)
Table 14.1.4.20	MRI Examination At V2 - Off-site FAS
Table 14.1.4.21	MRI Examination At V2 –Off-site PPS
Table 14.1.4.22	Pregnancy Test At V1 - Off-site FAS
Table 14.1.4.23	Pregnancy Test At V1 – Off-site Per Protocol Set (Off-site PPS)
Table 14.1.4.24	Pregnancy Test At V2 (if V2 performed more than one day after V1) - Off-site FAS
Table 14.1.4.25	Pregnancy Test At V2 (if V2 performed more than one day after V1) –Off-site PPS
14.1.5 COMPLIANCE	
Table 14.1.5.1	Total volume of IMP administered –Off-site PPS
Table 14.1.5.2	Preload Bolus administration –Off-site PPS

14.2 EFFICACY

14.2.1 PRIMARY ANALYSIS

Table 14.2.1.1	Technical adequacy of perfusion CBV map by off-site readers by treatment arm assigned at randomization – All Randomized and Treated Patients Set (ARTPS)
Table 14.2.1.2	Technical adequacy of perfusion CBV map by off-site readers by treatment arm assigned at randomization and by grade (stratification variable at randomization) – All Randomized and Treated Patients Set (ARTPS)
Table 14.2.1.3	Technical adequacy of perfusion CBV map by treatment arm assigned at randomization – Off-site PPS
Table 14.2.1.4	Technical adequacy of perfusion CBV map by treatment arm assigned at randomization and by grade (stratification variable at randomization) – Off-site PPS
Table 14.2.1.5	Technical adequacy of perfusion CBV map by treatment arm assigned at randomization – Off-site FAS
Table 14.2.1.6	Technical adequacy of perfusion CBV map by treatment arm assigned at randomization and by grade (stratification variable at randomization) – Off-site FAS
Table 14.2.1.7	Diagnostic quality of CBV map by treatment arm assigned at randomization – Off-site PPS
Table 14.2.1.8	Diagnostic quality of CBV map by treatment arm assigned at randomization and by grade (stratification variable at randomization) – Off-site PPS
Table 14.2.1.9	Diagnostic quality of CBV map by treatment arm assigned at randomization – Off-site FAS
Table 14.2.1.10	Diagnostic quality of CBV map by treatment arm assigned at randomization and by grade (stratification variable at randomization) – Off-site FAS

14.2.2 SECONDARY ANALYSES

Table 14.2.2.1	Intra-reader variability - Diagnostic quality of CBV map by treatment arm assigned at randomization – Off-site PPS
----------------	--

CONFIDENTIAL	STATISTICAL ANALYSIS PLAN N° GDX-44-016 VERSION N° 4.0 (REF I011622)	F015830-03 Page 31 / 35
--------------	--	----------------------------

Table 14.2.2.2 Intra-reader variability - Diagnostic quality of CBV map by treatment arm assigned at randomization – Off-site FAS

Table 14.2.2.3 Inter-reader variability - Diagnostic quality of CBV map by treatment arm assigned at randomization – Off-site PPS

Table 14.2.2.4 Inter-reader variability - Diagnostic quality of CBV map by treatment arm assigned at randomization – Off-site FAS

Table 14.2.2.5 Technical adequacy of perfusion CBV map by on-site readers by treatment arm assigned at randomization – All Randomized Patients Set (ARPS)

Table 14.2.2.6 Technical adequacy of perfusion CBV map by on-site readers by treatment arm assigned at randomization and by grade (stratification variable at randomization) – All Randomized Patients Set (ARPS)

Table 14.2.2.7 Technical adequacy of perfusion CBV map by treatment arm assigned at randomization – On-site PPS

Table 14.2.2.8 Technical adequacy of perfusion CBV map by treatment arm assigned at randomization and by grade (stratification variable at randomization) – On-site PPS

Table 14.2.2.9 Diagnostic quality of CBV map readers by treatment arm assigned at randomization – On-site PPS

Table 14.2.2.10 Diagnostic quality of CBV map by treatment arm assigned at randomization and by grade (stratification variable at randomization) – On-site PPS

Table 14.2.2.11 Technical adequacy of perfusion CBV map by treatment arm assigned at randomization – On-site FAS

Table 14.2.2.12 Technical adequacy of perfusion CBV map by treatment arm assigned at randomization and by grade (stratification variable at randomization) – On-site FAS

Table 14.2.2.13 Diagnostic quality of CBV map by treatment arm assigned at randomization – On-site FAS

Table 14.2.2.14 Diagnostic quality of CBV map generated assessed by treatment arm assigned at randomization and by grade (stratification variable at randomization) – On-site FAS

Table 14.2.2.15 rCBV by treatment arm assigned at randomization and by grade (stratification variable at randomization) – Comparison between arms – Off-site PPS

Table 14.2.2.16 rCBV by treatment arm assigned at randomization and by grade (stratification variable at randomization) – Comparison within arms – Off-site PPS

Table 14.2.2.17 rCBV by treatment arm assigned at randomization and by grade (stratification variable at randomization) – Comparison between arms – Off-site FAS

Table 14.2.2.18 rCBV by treatment arm assigned at randomization and by grade (stratification variable at randomization) – Comparison within arms – Off-site FAS

Table 14.2.2.19 rCBV by treatment arm assigned at randomization and by grade (according to histopathology) – Comparison between arms – Off-site PPS - Patients With a Detected Lesion Matching Histopathology

Table 14.2.2.20 rCBV by treatment arm assigned at randomization and by grade (according to histopathology) – Comparison within arms – Off-site PPS - Patients With a Detected Lesion Matching Histopathology

Table 14.2.2.21 rCBV by treatment arm assigned at randomization and by grade (according to histopathology) – Comparison between arms – Off-site FAS - Patients With a Detected Lesion Matching Histopathology

Table 14.2.2.22 rCBV by treatment arm assigned at randomization and by grade (according to histopathology) – Comparison within arms – Off-site FAS - Patients With a Detected Lesion Matching Histopathology

Table 14.2.2.23 Grade assessed by off-site readers (based on rCBV) by treatment arm assigned at randomization and by grade (stratification variable at randomization) – Off-site PPS

Table 14.2.2.24 Grade assessed by off-site readers (based on rCBV) by treatment arm assigned at randomization and by grade (stratification variable at randomization) – Off-site FAS

CONFIDENTIAL	STATISTICAL ANALYSIS PLAN N° GDX-44-016 VERSION N° 4.0 (REF I011622)	F015830-03 Page 32 / 35
--------------	--	----------------------------

Table 14.2.2.25 Grade assessed by off-site readers (based on rCBV) by treatment arm assigned at randomization and by grade (according to histopathology) – Off-site PPS - Patients With a Detected Lesion Matching Histopathology

Table 14.2.2.26 Grade assessed by off-site readers (based on rCBV) by treatment arm assigned at randomization and by grade (according to histopathology) – Off-site FAS - Patients With a Detected Lesion Matching Histopathology

Table 14.2.2.27 Reliability of the T2* signal intensity time curve for diagnosis and level of diagnosis confidence by treatment arm assigned at randomization at Lesion Level – Off-site PPS

Table 14.2.2.28 Reliability of the T2* signal intensity time curve for diagnosis and level of diagnosis confidence by treatment arm assigned at randomization and by grade (stratification variable at randomization) at Lesion Level – Off-site PPS

Table 14.2.2.29 Reliability of the T2* signal intensity time curve for diagnosis and level of diagnosis confidence by treatment arm assigned at randomization at Lesion Level – Off-site FAS

Table 14.2.2.30 Reliability of the T2* signal intensity time curve for diagnosis and level of diagnosis confidence by treatment arm assigned at randomization and by grade (stratification variable at randomization) at Lesion Level – Off-site FAS

Table 14.2.2.31 Reliability of the T2* signal intensity time curve for diagnosis and level of diagnosis confidence by treatment arm assigned at randomization at Lesion Level – On-site PPS

Table 14.2.2.32 Reliability of the T2* signal intensity time curve for diagnosis and level of diagnosis confidence assessed by treatment arm assigned at randomization and by grade (stratification variable at randomization) at Lesion Level – On-site PPS

Table 14.2.2.33 Reliability of the T2* signal intensity time curve for diagnosis and level of diagnosis confidence assessed by treatment arm assigned at randomization at Lesion Level – On-site FAS

Table 14.2.2.34 Reliability of the T2* signal intensity time curve for diagnosis and level of diagnosis confidence assessed by treatment arm assigned at randomization and by grade (stratification variable at randomization) at Lesion Level – On-site FAS

Table 14.2.2.35 Full-Width at Half-Maximum and Maximum signal drop by treatment arm assigned at randomization at Lesion Level – Off-site PPS

Table 14.2.2.36 Full-Width at Half-Maximum and Maximum signal drop by treatment arm assigned at randomization and by grade (stratification variable at randomization) at Lesion Level – Off-site PPS

Table 14.2.2.37 Full-Width at Half-Maximum and Maximum signal drop by treatment arm assigned at randomization at Lesion Level – Off-site FAS

Table 14.2.2.38 Full-Width at Half-Maximum and Maximum signal drop by treatment arm assigned at randomization and by grade (stratification variable at randomization) at Lesion Level – Off-site FAS

